## 8.2 Dose Modifications

- If study drug/s is(are) held for >6 weeks, study drug/s will be discontinued.
- Any patients with autoimmune toxicity who require additional immune suppressive treatment beyond steroids should go off study drug/s.
- Patients may be dose-delayed for toxicity evaluation and restarted depending on results.
- Any patient started on corticosteroids initially for a presumed autoimmune adverse event, and subsequently found to not have an autoimmune etiology of their adverse event, may resume therapy after a 2 week observation period without recurrence of symptoms.
- Study drug/s should not be restarted until steroids have been tapered down to 5mg of prednisone equivalent.
- Patients requiring > two dose delays for the same event should go off study drug.
- Descriptors below utilize CTCAE version 4.03. AERs reporting may be required for some adverse events (See [Section 9.0](#))

### 8.2.1 Dose Levels

See [Section 7.0](#) and [Section 7.2](#) for the dosing schema for both arms. **No dose reductions will be made during this study, only dose delays.** Therefore there is only 1 dose level.

**The following tables provide protocol specific instructions for continuing administration of the investigational agent.**

*Generally we strongly encourage early evaluation, withholding drug, and appropriate treatment as indicated in the management tables and following event specific guidelines.*

### 8.2.2 Dose Modification

Skin Rash and Oral Lesions	Management/Next Dose for Nivolumab and Ipilimumab
Grade 1	Continue on protocol therapy*
Grade 2	Continue on protocol therapy.*
Grade 3	Hold** until ≤ Grade 1. Resume nivolumab/ipilimumab at same level*
Grade 4	Off protocol therapy
*Steroid use does not require discontinuation of protocol therapy.	
**Any grade Steven Johnson syndrome requires discontinuation of protocol therapy.	
Recommended management: See Skin AE management algorithm	

Liver Function ALT AST Bilirubin	Management/Next Dose for Nivolumab and Ipilimumab
Grade 1	Continue protocol therapy*
Grade 2	Hold therapy until ≤ grade 1 then restart nivolumab/ipilimumab at same dose.*
Grade 3	Off protocol therapy
Grade 4	Off protocol therapy
*Steroid use does require discontinuation of protocol therapy.	
Recommended management: see Hepatitis AE management algorithm	

Colitis**	Management/Next Dose for Nivolumab and Ipilimumab
Grade 1	Continue protocol therapy*
Grade 2	Hold therapy until $\leq$ Grade 1*, then restart nivolumab at same dose. Discontinue ipilimumab.
Grade 3	Off protocol therapy.
Grade 4	Off protocol therapy.
See GI AE Algorithm for management of symptomatic colitis. *Steroid use does not require discontinuation of protocol therapy. **Follow this table for diarrhea when the workup shows objective evidence of autoimmune colitis.	
Recommended management: see GI AE management Algorithm	

Diarrhea**	Management/Next Dose for Nivolumab and Ipilimumab
Grade 1	Continue protocol therapy
Grade 2	Hold until $\leq$ Grade 1*, then restart nivolumab/ipilimumab at same dose.
Grade 3	Hold until $\leq$ Grade 1*, then restart nivolumab/ipilimumab at same dose.
Grade 4	Hold until $\leq$ Grade 1*, then restart nivolumab/ipilimumab at same dose.
*Steroid use does not require discontinuation of protocol therapy. **Follow this table for diarrhea when the workup shows no objective evidence of autoimmune colitis	

Pancreatitis**	Management/Next Dose for Nivolumab and Ipilimumab
Grade 2	Continue on protocol therapy*
Grade 3	Hold therapy until $\leq$ grade 2 then restart nivolumab/ipilimumab at same dose.*
Grade 4	Off protocol therapy
*Steroid use does require discontinuation of protocol therapy. **Patients who have asymptomatic amylase or lipase elevation may have a self-limited course and may continue therapy.	

Pneumonitis	Management/Next Dose for Nivolumab and Ipilimumab
Grade 1	Hold dose pending evaluation. Resume nivolumab/ipilimumab if lymphocytic pneumonitis is excluded.*
Grade 2	Hold until $\leq$ Grade 1*, then restart nivolumab/ipilimumab at same dose.
Grade 3	Off protocol therapy.
Grade 4	Off protocol therapy
*Steroid use does require discontinuation of protocol therapy.	
Recommended management: See Pulmonary Adverse Event Management Algorithm	

Gastritis, nausea, vomiting	Management/Next Dose for Nivolumab and Ipilimumab
Grade 1	Continue protocol therapy*
Grade 2	Hold pending evaluation for gastritis duodenitis and other immune adverse events or other causes. Resume nivolumab/ipilimumab at same dose level after resolution to Grade $\leq$ 1.*
Grade 3	Hold pending evaluation until $\leq$ Grade 1. Resume nivolumab at same dose level.* If symptoms do not resolve within 7 days with symptomatic treatment, patients should go off nivolumab. Discontinue ipilimumab.
Grade 4	Off protocol therapy
*Steroid use does not require discontinuation of protocol therapy.	

Fatigue	Management/Next Dose for Nivolumab and Ipilimumab
Grade 1	Continue protocol therapy.
Grade 2	Continue protocol therapy.
Grade 3	Hold until $\leq$ Grade 2. Resume nivolumab/ipilimumab at same dose level.*
*Steroid use does not require discontinuation of protocol therapy.	

Neurologic events **	Management/Next Dose for Nivolumab and Ipilimumab
Grade 1	Hold dose pending evaluation. Once evaluation is complete, resume nivolumab/ipilimumab at same dose level.*
Grade 2	Hold dose pending evaluation and observation. Hold until $\leq$ Grade 1 and then resume nivolumab/ipilimumab at same dose level.*
Grade 3	Off protocol therapy
Grade 4	Off protocol therapy
*Steroid use does require discontinuation of protocol therapy. **Patients with any grade CNS events of aseptic meningitis, encephalitis, symptomatic hypophysitis, or myopathy, polymyositis, rhabdomyolysis, peripheral demyelinating neuropathy, cranial neuropathy (other than peripheral n. VII), GB syndrome, myasthenia gravis should be off study once diagnosed.	
Recommended management: See Neurologic Adverse Event Management Algorithm	

Endocrine Toxicity**	Management/Next Dose for Nivolumab and Ipilimumab
Grade 1	Continue protocol therapy.*
Grade 2	Hold until $\leq$ Grade 1 and patients are on a stable replacement hormone regimen, then resume nivolumab/ipilimumab at same dose level.*
Grade 3	Off protocol therapy.***
Grade 4	Off protocol therapy
*Steroid use for isolated thyroid disease or testosterone deficiency does not require discontinuation of protocol therapy. Steroid use for any other form of endocrine toxicity does require discontinuation of therapy. **Note all patients with symptomatic pituitary enlargement, exclusive of hormone deficiency, but including severe headache or enlarged pituitary on MRI should be considered grade 3 events and removed from protocol therapy. Also, note patients with thyroiditis may be retreated with immunotherapy while on replacement therapy. ***Isolated thyroid or testosterone deficiency may be treated as grade 2 if there are no other associated deficiencies and adrenal function is monitored.	
Recommended management: See Endocrine Management Algorithm	

Fever	Management/Next Dose for Nivolumab
Grade 1	Continue protocol therapy. May hold if needed for evaluation, then resume nivolumab/ipilimumab at same dose level.*
Grade 2	Hold until $\leq$ Grade 1. Resume nivolumab/ipilimumab at same dose level.*
Grade 3	Hold until $\leq$ Grade 1. Resume nivolumab/ipilimumab at same dose level.*
Grade 4	Off treatment
*Steroid use does not require discontinuation of protocol therapy.	
See Appendix V regarding infusion reactions.	

Renal toxicity: Creatinine increased, hematuria	Management/Next Dose for Nivolumab and Ipilimumab
Grade 1	Continue protocol therapy.*
Grade 2	Hold until $\leq$ Grade 1. Resume nivolumab/ipilimumab at same dose level.*
Grade 3	Off protocol therapy.
Grade 4	Off protocol therapy
*Steroid use does require discontinuation of protocol therapy.	
Recommended management: AE management guidelines	

Infusion Reaction	Management/Next Dose for Nivolumab and Ipilimumab
Grade 1	Continue protocol therapy.*
Grade 2	Hold until $\leq$ Grade 1. Resume nivolumab/ipilimumab at same dose level.*
Grade 3	Off protocol therapy.
Grade 4	Off protocol therapy
*Steroid use does not require discontinuation of protocol therapy.	
Recommended management: see Section 8.1.9 and Appendix V management guidelines	

Cardiac *	Management/Next Dose for BMS-936558 (Nivolumab) + Ipilimumab Cardiac Toxicities
<math>\leq</math> Grade 1	Hold dose pending evaluation and observation.** Evaluate for signs and symptoms of CHF, ischemia, arrhythmia or myositis. Obtain history EKG, CK (for concomitant myositis), CK-MB. Repeat troponin, CK and EKG 2-3 days. If troponin and labs normalize may resume therapy. If labs worsen or symptoms develop then treat as below. Hold pending evaluation.
Grade >2 with suspected myocarditis	Hold dose.** Admit to hospital. Cardiology consult. Rule out MI and other causes of cardiac disease. Cardiac Monitoring. Cardiac Echo. Consider cardiac MRI and cardiac biopsy. Initiate high dose methylprednisolone. If no improvement within 24 hours, add either infliximab, ATG or tacrolimus. Consult algorithm for more details. Resume therapy if there is a return to baseline and myocarditis is excluded or considered unlikely.
Grade >2 with confirmed myocarditis	Off protocol therapy. Admit to CCU (consider transfer to nearest Cardiac Transplant Unit). Treat as above. Consider high dose methylprednisolone. Add ATG or tacrolimus if no improvement. Off treatment.
*Including CHF, LV systolic dysfunction, Myocarditis, CPK, and troponin	
**Patients with evidence of myositis without myocarditis may be treated according as “other event”	
Note: The optimal treatment regimen for immune mediated myocarditis has not been established. Since this toxicity has caused patient deaths, an aggressive approach is recommended.	

ALL OTHER EVENTS (Note 1)	Management/Next Dose for Nivolumab and Ipilimumab
≤ Grade 1	No change in dose
Grade 2	Hold until ≤ Grade 1, then resume nivolumab/ipilimumab at same dose level.
Grade 3	Off protocol therapy (exceptions noted below in note 2)
Grade 4	Off protocol therapy

Note: 1. Modifications are applicable to toxicity that is deemed related to study drug (attribution of possible, probable, or definite).
 
Note 2. For any grade 2 drug-related uveitis or eye pain or blurred vision that does not respond to topical therapy and does not improve to Grade 1 severity within the re-treatment period OR requires systemic treatment, nivolumab and ipilimumab should be discontinued.
	
Recommended management: As clinically indicated	

All other Grade  $\geq$  3 events including anemia, hyponatremia, hypernatremia, hypokalemia, hyperkalemia, hypocalcemia, hypercalcemia, hypomagnesemia, hypermagnesemia, hypoglycemia, hyperglycemia, elevated amylase or lipase that is deemed unrelated to drug (attribution of unrelated or unlikely) does not require change in dose.

Lymphopenia of any grade does not require change in dose.

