**Hepatitis C can be defined as:**

1. Hepatitis C AB positive
  2. Presence of HCV RNA
- Known active pulmonary disease with hypoxia defined as
    1. Oxygen saturation < 85% on room air or
    2. Oxygen saturation <88% despite supplemental oxygen

\_\_\_ **3.3.5 Concomitant Medications:**

No systemic treatment with either corticosteroids (> 10 mg daily prednisone equivalents) or other immunosuppressive medications within 14 days of registration.

\_\_\_ **3.3.6 Not pregnant and not nursing,** because this study involves an agent that has known genotoxic, mutagenic and teratogenic effects.

Therefore, for women of childbearing potential only, a negative pregnancy test done  $\leq 7$  days prior to registration is required.

\_\_\_ **3.3.7 Age  $\geq 18$  years**

\_\_\_ **3.3.8 ECOG Performance Status 0 or 1.**

\_\_\_ **3.3.9 Required Initial Laboratory Values:**

Absolute Neutrophil Count (ANC)	$\geq 1,500/\text{mm}^3$
Platelet Count	$\geq 100,000/\text{mm}^3$
Creatinine	$\leq 1.5 \times$ upper limit of normal (ULN) OR
Calc. Creatinine Clearance	$> 45 \text{ mL/min}^*$
Total Bilirubin	$\leq 1.5 \times$ upper limit of normal (ULN)**
AST / ALT	$\leq 3 \times$ upper limit of normal (ULN)
TSH	WNL***

\* Using the lean body mass formula only (Modified Cockcroft and Gault; Shargel and Yu 1985)

\*\* In absence of Gilbert disease (Total Bilirubin  $\leq 3 \times$  ULN with Gilbert). Also, if hyperbilirubinemia is clearly attributed to liver metastases total bilirubin  $\leq 3 \times$  ULN is permitted

\*\*\* Supplementation is acceptable to achieve a TSH WNL. In patients with abnormal TSH if Free T4 is normal and patient is clinically euthyroid, patient is eligible.

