#### 3.4.5 ECOG Performance Status 0 or 1.

#### 3.4.6 Required Laboratory Values:

Absolute Neutrophil Count (ANC)	$\geq$ 1,500/mm 
Platelet Count	$\geq$ 100,000/mm 
Creatinine	$\leq$ 1.5 x upper limit of normal (ULN) OR
Calc. Creatinine Clearance	$>$ 45 mL/min*
Total Bilirubin	$\leq$ 1.5 x upper limit of normal (ULN)**
AST / ALT	$\leq$ 3 x upper limit of normal (ULN)
TSH	WNL***

- \* Using the lean body mass formula only (Modified Cockcroft and Gault; Shargel and Yu 1985)

- \*\* In absence of Gilbert disease (Total Bilirubin  $\leq 3 \times$  ULN with Gilbert). Also, if hyperbilirubinemia is clearly attributed to liver metastases total bilirubin  $\leq 3 \times$  ULN is permitted
- \*\*\* Supplementation is acceptable to achieve a TSH WNL. In patients with abnormal TSH if Free T4 is normal and patient is clinically euthyroid, patient is eligible.

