### Pre-Study and Pre-Crossover (re-registration) Testing Intervals

- To be completed  $\leq 16$  DAYS before registration and re-registration: All laboratory studies, history and physical.
- To be completed  $\leq 28$  DAYS before registration: Any X-ray, scan of any type or ultrasound which is utilized for tumor measurement per protocol
- To be completed  $\leq 42$  DAYS before registration and re-registration: Any baseline exams used for screening, or any X-ray, scan of any type or ultrasound of uninvolved organs which is not utilized for tumor measurement.

	Prior to Registration AND Prior to Re-Registration *	Arm 1 (Nivolumab alone): Every 2 weeks	Arm 2 AND Crossover Patients Every 3 weeks x 12 weeks, then every 2 weeks	Post treatment follow up**	At PD, withdrawal, or removal***
Tests & Observations					
History and physical, weight, PS****	X	X	X	X	X
Height	X				
Pulse, Blood Pressure	X	X	X		
Oxygen Saturation †	X	X	X	X	
Adverse Event Assessment $\pi$	X	X	X	X	
EKG, Echo or MUGA, CPK, troponin	X (F)				
Registration Fatigue/Uniscale Assessment	X(1)				
Laboratory Studies					
Complete Blood Count, Differential, Platelets	X	X (2)	X (2)	X	
Chemistry $\Psi$	X	X (2)	X (2)	X	
TSH	X	A(2)	A(2)		
Lipase		B(2)	B(2)		
Serologic Hepatitis B Surface Ag and Hepatitis C ab (physician discretion, not required)	X				
Serum or Urine HCG	X(3)				
Urinalysis		B(2)	B(2)		
Staging					
Central Pathology review for eligibility	X(4)				
CT or MRI of chest and of regions of tumor involvement	X(5)	C, D	C, D,E	C	X
Correlative studies: For patients who consent to participate					
Tissue samples (4)	Baseline, and end of cycle 1. See Section 6.2				
Blood samples (4)	Weeks 1-16, PD/withdrawal/removal. See Section 6.2				

- \* Labs completed prior to registration may be used for day 1 of cycle 1 tests if obtained  $\leq 16$  days prior to treatment. Labs completed prior to re-registration may be used for day 1 of cycle 1 if obtained  $\leq 16$  days prior to treatment.
- \*\* Physical examination, adverse event assessment, labs (CBC and chem), and staging scans (if due per footnote C) are required 4 weeks (+/- 7 days) after the end of treatment.

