### 9.1 Routine adverse event reporting (solicited)

Adverse event data collection and reporting, which are required as part of every clinical trial are done to ensure the safety of patients enrolled in the studies as well as those who will enroll in future studies using similar agents. Adverse events are reported in a routine manner at scheduled times according to the study calendar in [Section 5.0](#). For this trial, "Adverse Events: Baseline", "Adverse Events: Solicited" and "Adverse Events: Other" are used for routine AE reporting in Rave.

**Solicited Adverse Events:** The following adverse events are considered "expected" and their presence/absence should be solicited, and severity graded, at baseline and for each cycle of treatment.

CTCAE v4.0 Term	CTCAE v4.0 System Organ Class (SOC)
Hypothyroidism	Endocrine disorders
Abdominal Pain	Gastrointestinal disorders
Diarrhea	Gastrointestinal disorders
Nausea	Gastrointestinal disorders
Fatigue	General disorders and administration site conditions
Blood bilirubin increased	Investigations
Anorexia	Metabolism and nutrition disorders
Arthralgia	Musculoskeletal and connective tissue disorders
Cough	Respiratory, thoracic, and mediastinal disorders
Dyspnea	Respiratory, thoracic and mediastinal disorders

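### The 8.2.2 liver table has no baseline clause for patients deliberately enrolled with bilirubin up to 3 x ULN; read literally, a stable value holds dose 2 and ends treatment after one dose.

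*Combined protocol and SAP*

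**What the plan says.** **Entry.** The general limit for total bilirubin in Section 3.3.9 is 1.5 x ULN. Two groups may enter at up to 3 x ULN: patients with Gilbert disease, and, in the footnote's words, "if hyperbilirubinemia is clearly attributed to liver metastases total bilirubin" up to that level is allowed. Section 3.4.6 repeats both allowances for re-registration to crossover; its footnote opens "In absence of Gilbert disease".

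**Dose 1.** The Section 5.0 calendar states "Labs completed prior to registration may be used for day 1 of cycle 1 tests if obtained" no more than 16 days before treatment. The first dose can therefore be given on the eligibility value.

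**Later doses.** The liver table in Section 8.2.2 covers ALT, AST and bilirubin, and its column heading refers to the next dose. Grade 1 continues, Grades 3 and 4 come off protocol therapy, and for Grade 2 the instruction is "Hold therapy until ≤ grade 1 then restart nivolumab/ipilimumab at same dose". The table does not mention baseline, Gilbert disease, liver metastases or attribution.

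**Time limit.** Section 8.2 states "If study drug/s is(are) held for >6 weeks, study drug/s will be discontinued".

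**Texts pointing the other way.** Section 8.2 also says "Patients may be dose-delayed for toxicity evaluation and restarted depending on results". The liver table refers to the hepatic algorithm in Appendix III, whose visible text tells the physician to treat a non-inflammatory cause and go on with immunotherapy. Section 8.1 describes the Appendix III algorithms as recommended guidance.

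**The concern.** The eligibility section accepts a raised bilirubin with a known, non-immune cause. The dosing section then treats the same value as a toxicity that must fall before the next dose. A patient with Gilbert disease may never reach Grade 1, so on the literal rule the hold runs past 6 weeks and treatment ends although nothing has changed since entry.

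Three consequences follow for such a patient:

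- Under Section 13.3 the patient has begun treatment and counts in the response denominator.
- Under Section 12.3 only patients who never received study treatment are replaceable, so this patient is not.
- An Arm 1 patient fails two criteria in Section 3.4.2: removal must have been for progression, and at least 10 weeks of nivolumab must have been completed.

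Sites could also resolve the conflict differently, one stopping and another continuing for the same stable value.

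**Working it through.** The plan states no figure on this point, so the check sets the rules side by side and counts days.

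**1. Which entry values are caught.** Let c be the lower limit of Grade 2 bilirubin in multiples of ULN. Section 8.2 grades by CTCAE 4.03 but does not print c. The conflict covers entry values above c and up to 3 x ULN.

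| Assumed c | Exception-range values caught |
|---|---|
| 1.5 | all, >1.5 to 3 x ULN |
| 2.0 | >2.0 to 3 x ULN |
| 3.0 | none |

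The working assumption is c = 1.5, without adjustment for a raised baseline. ALT/AST has no allowance above 3 x ULN at entry; on the same assumed scale, 3 x ULN or less is Grade 1, so no conflict arises there.

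**2. Whether the value is seen at dose 2.** Section 9.1 lists raised bilirubin among the solicited events and says "their presence/absence should be solicited, and severity graded, at baseline and for each cycle of treatment". A cycle is 42 days, so that alone does not place a grading at dose 2. The Section 5.0 calendar does: chemistry, including total bilirubin, is drawn every 2 weeks in Arm 1 and every 3 weeks for the first 12 weeks in Arm 2 and crossover.

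**3. When the limit is passed.** If the hold starts when dose 2 is due, last day within the limit = day dose 2 is due + 42.

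- Arm 1: doses due days 1, 15, 29, 43, 57. 15 + 42 = 57, so the hold exceeds 6 weeks from day 58. Of the 4 doses due before day 57, 1 has been given.
- Arm 2 and crossover: doses due days 1, 22, 43, 64. 22 + 42 = 64, so the hold exceeds 6 weeks from day 65. Of the 3 combination doses due before day 64, 1 has been given.
- If the hold is instead counted from the last dose, the limit falls at 1 + 42 = day 43 in both schedules. The plan does not say which count applies. One dose has been given either way.

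**4. Crossover.** Ten completed weeks end at day 1 + 70 = day 71. Day 58 is earlier, so the 10-week minimum is missed even if weeks on hold are counted as treatment. The removal is also not for progression.

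**5. Whether another clause rescues the patient.**

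- The attribution limit (Note 1) belongs to the table for all other events, not to the liver table.
- The closing text of 8.2.2 on unrelated events concerns other events of Grade 3 or more, so it does not reach a Grade 2 bilirubin.
- The plan does write such exceptions elsewhere: for asymptomatic amylase or lipase, for lymphopenia, and, in the cardiac table, resumption on return to baseline when myocarditis is excluded or unlikely.

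**6. Worst-case effect on power, for illustration.** Power = P(X ≥ r) for X binomial(n, p1). With n = 38, r = 5, p1 = 0.20, this gives 0.901 (stated 90%). With n = 12, r = 2, p1 = 0.25, it gives 0.842 (stated 85%). If k patients per arm are certain non-responders, replace n by n − k:

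| k | n = 38 | n = 12 |
|---|---|---|
| 1 | 0.888 | 0.803 |
| 2 | 0.873 | 0.756 |

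The documents give no value for k, and one dose does not make non-response certain. These are bounds on an assumption, not an estimate.

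**The case against.** The strongest reply is that no sensible site would read the table alone. Patients admitted above 1.5 x ULN are exactly those whose cause is already known and non-inflammatory, and the algorithm named in the liver table says to continue for such a cause. Section 8.2 lets restart depend on the evaluation, and Section 8.1.10 speaks of evaluating changes in liver function. The hepatic flowchart is not shown in the text available, so it may contain a return-to-baseline rule that cannot be checked. A cautious hold is also defensible, since Section 10.3 says ipilimumab has not been studied at bilirubin above 1.5 to 3 x ULN.

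Much of this stands. The sensible reading is available, and it cannot be said that patients would in practice be stopped. It does not settle the matter, though. Section 8.2.2 introduces the tables as this protocol's own dosing instructions, while the algorithms are recommended guidance. The general restart sentence states no condition; the table states one. Nor can the algorithm be assumed to override the table. Its footnote permits delay instead of discontinuation up to bilirubin 5 x ULN, whereas the table takes Grade 3 off therapy; if Grade 3 starts below 5 x ULN, these also differ.

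A reader might extend the point to creatinine, because 3.3.9 accepts a value above 1.5 x ULN when clearance exceeds 45 mL/min and the renal table ("Creatinine increased, hematuria") has the same hold. The documents do not support that extension: they give no upper bound for creatinine admitted this way and no grading basis, and such patients would be rare.

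**Conclusion.** The liver table and the hepatic algorithm give different answers for patients enrolled under the bilirubin exceptions, and the table, read literally, can end treatment after one dose for an unchanged value. This rests on Grade 2 starting below 3 x ULN and on the entry value staying at Grade 2. The number of such patients is not given and is probably small. The gap is minor but worth correcting.

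Two stronger readings do not follow:

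- **A response is lost.** The earliest nominal confirmation is day 71 (first scan day 43, plus 28 days), after the day 58 or day 65 stop. But the Section 5.0 calendar carries scans into post-treatment follow-up, and Section 13.3 cuts off assessments at crossover or other anti-cancer therapy, not when drug stops. The dates do not show a missed response.
- **The design's error rates are wrong.** Nothing here shows that. The power figures above depend on an assumed count and assumed non-response.

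**What to change.** Add one footnote to the bilirubin entry of the 8.2.2 liver table, for patients enrolled under the 3.3.9 or 3.4.6 bilirubin exceptions only:

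- A stable bilirubin at or below the qualifying baseline, with no concurrent ALT/AST rise of Grade 2 or more and no suspected immune hepatitis, does not by itself require a hold.
- The hold and off rules apply to worsening above that baseline, and to any renewed rise to Grade 2 or more after bilirubin has improved on treatment.
- A patient held for worsening may resume on return to baseline once immune hepatitis is excluded.

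The renewed-rise clause is needed. A patient who enters at 2.8 x ULN, falls to normal and then rises to 2.7 x ULN from immune hepatitis would escape the bilirubin hold if every value at or below baseline were exempt.

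ALT/AST rules and all other patients stay as they are. The change needs no extra patients, visits or tests, because bilirubin is already graded at baseline. Its price is slightly less conservative dosing in a small subgroup, in a range where Section 10.3 says ipilimumab is unstudied. Small fluctuations above baseline would still cause short holds.

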### 3.3.3 Prior Treatment

- $\geq 1$  prior systemic therapy for sarcoma, including adjuvant systemic therapy.
- No prior therapy with ipilimumab or nivolumab, or any agent targeting PD-1, PD-L1 or CTLA-4.
- No treatment with biologic therapy, immunotherapy, chemotherapy, investigational agent for malignancy, or radiation  $\leq 28$  days before study registration. No treatment with nitrosourea or mitomycin  $\leq 42$  days before study registration. For GIST, tyrosine kinase inhibitor can be continued for up to 3 days prior to initiation of study treatment.
- Patients should have resolution of any toxic effects of prior therapy (except alopecia) to NCI CTCAE, Version 4.0, grade 1 or less.

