- \*\*\* Patients who do not progress on treatment (i.e. removal for toxicity or withdrawal of consent) are followed every 6 months for both survival and disease status for at least three years post-randomization or until death, whichever comes first. Upon progressive disease (at any time), survival information is required every 6 months for 3 years. See also [Section 12](#).
- \*\*\*\* Drug dosages need not be changed unless the calculated dose changes by  $\geq 10\%$ .
- † Oxygen saturation should be assessed at rest and after 1 minute walk.
- $\pi$  Solicited AEs are to be collected starting at baseline until off treatment (See [Section 9.1](#)). Routine AEs are to be collected starting after registration. See [Section 9.3](#) for expedited reporting of SAEs.
- $\Psi$  Albumin, alkaline phosphatase, total bilirubin, bicarbonate, BUN, calcium, chloride, creatinine, glucose, potassium, total protein, SGOT[AST], SGPT[ALT], sodium.
  - 1 To be completed after pre-registration and prior to registration ( $\leq 21$  days prior to treatment), see [Section 1.9](#) and [Appendix I](#). NOT required for re-registration.
  - 2 Labs may be performed +/- 3 days from date required.
  - 3 For women of childbearing potential (see [Section 3.2](#)). Must be done  $\leq 7$  days prior to registration. Also, must be done  $\leq 7$  days prior to re-registration.
  - 4 See [Section 6.2](#). Central pathology review is only required for registration, not required for re-registration.
  - 5 Baseline scans can include either: 1) a CT, spiral CT, or MRI, or 2) an FDG-PET scan and diagnostic CT performed with both IV and oral contrast, and the CT acquired with 5 mm or less slice thickness. Supporting documentation is to be submitted, per [Section 6.1.1](#).
- A Every 6 to 8 weeks.
- B Perform every 4 weeks x 4 in arm 1 (nivolumab alone). Perform every 3 weeks x 4, then every 2 weeks x 1 in arm 2 and crossover to dual agent therapy (nivolumab + ipilimumab).

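### The liver hold rule in 8.2.2 has no exception for a stable bilirubin in on-treatment patients who were knowingly admitted with up to 3 x ULN

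*Combined protocol and SAP*

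**What the plan says.** **Entry.** Section 3.3.9 (registration) and Section 3.4.6 (re-registration for crossover) limit total bilirubin to 1.5 x ULN. The footnote raises the limit to 3 x ULN for Gilbert disease and then adds a second allowance: "Also, if hyperbilirubinemia is clearly attributed to liver metastases total bilirubin" may again be up to 3 x ULN. Section 3.3.3 treats toxicity left over from earlier treatment separately: "Patients should have resolution of any toxic effects of prior therapy (except alopecia) to NCI CTCAE, Version 4.0, grade 1 or less". The bilirubin allowance is therefore deliberate and concerns causes other than drug toxicity.

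**On treatment.** The calendar in Section 5.0 repeats chemistry on the dosing schedule. The panel begins "Albumin, alkaline phosphatase, total bilirubin, bicarbonate, BUN, calcium, chloride, creatinine". In 8.2.2 the table headed Liver Function ALT AST Bilirubin acts on grade alone. For grade 2 it says "Hold therapy until ≤ grade 1 then restart nivolumab/ipilimumab at same dose"; grades 3 and 4 go off protocol therapy. Apart from the pointer to the hepatitis algorithm, its only note concerns steroids. It does not mention the entry value, Gilbert disease, liver metastases or attribution.

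**Limits on holding.** Section 8.2.1 allows delays but no dose reductions. Section 8.2 adds "If study drug/s is(are) held for >6 weeks, study drug/s will be discontinued" and "Patients requiring > two dose delays for the same event should go off study drug".

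**Grading.** Section 8.2 applies CTCAE 4.03 to the tables. The numerical cut-offs are not reproduced.

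**The concern.** The entry criteria and the liver table can point in opposite directions for the same bilirubin value. A patient with Gilbert disease or liver metastases is accepted in the knowledge that bilirubin is raised for a reason unrelated to study drug. At an on-treatment test the same unchanged value can be grade 2, and the table then stops both drugs until bilirubin falls below where it was at entry. Nothing about the underlying cause makes that fall likely.

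At stake is treatment for a small group the protocol chose to include. They could lose doses, and after more than 6 weeks lose therapy altogether, with no change in liver function. Consistency is also at stake: one site may follow the table and hold, while another treats the entry value as the patient's normal level and doses. The same applies to patients who cross over under 3.4.6.

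**Working it through.** The plan states no figure for this, so there is none to reproduce. The check compares the entry band with the hold rule, both in multiples of ULN.

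**Inputs from the protocol**
- Exempt entry band: above 1.5 and up to 3.0 x ULN (3.3.9, 3.4.6).
- Restart condition: grade 1 or less (8.2.2, liver table).
- Discontinuation: hold longer than 6 weeks (8.2).

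**Assumption (not in the protocol).** CTCAE 4.03 grades bilirubin against ULN, with a grade 1 ceiling *c*. I vary *c* from 1.5 to 3.0 x ULN.

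**Step 1: does an unchanged value meet the hold rule?** It does for every entry value *b* with *c* < *b* ≤ 3.0. With *c* = 1.5 the whole exempt band is caught. With *c* = 2.0 it is the part above 2.0, and with *c* = 2.5 the part above 2.5. With *c* = 3.0 nothing is caught.

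**Step 2: how far must bilirubin fall before restart?** Fall = max(0, 1 − *c*/*b*).

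| Assumed grade 1 ceiling *c* | Entry *b* = 2.0 | *b* = 2.5 | *b* = 3.0 |
|---|---|---|---|
| 1.5 | 1 − 1.5/2.0 = 25% | 1 − 1.5/2.5 = 40% | 1 − 1.5/3.0 = 50% |
| 2.0 | 0% | 1 − 2.0/2.5 = 20% | 1 − 2.0/3.0 = 33% |
| 2.5 | 0% | 0% | 1 − 2.5/3.0 = 17% |
| 3.0 | 0% | 0% | 0% |

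**Step 3: alternative grading.** If grade were set relative to an abnormal baseline, an unchanged value has ratio *b*/*b* = 1.0 and would not be grade 2. The conflict then disappears. The liver table does not say that grading works this way.

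**Step 4: consequence for a stable patient.** The hold never meets its release condition. Six weeks is 42 days, one full cycle: three doses on a two-week schedule (6/2) or two on a three-week schedule (6/3). Beyond that the drug is discontinued. The limit on repeated delays matters only for a value that moves in and out of grade 2; a constant value gives one continuous hold.

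**Step 5: does other text supply the exception?**
- The note confining modifications to drug-related toxicity is attached to the ALL OTHER EVENTS table, not the liver table.
- The paragraph after the tables exempts other unrelated events of grade 3 or higher. A grade 2 bilirubin has its own table.
- The general remark in 8.2 that delayed patients may be restarted depending on results does not displace the liver table's explicit threshold.
- Section 9.1 has raised bilirubin graded at baseline and each cycle, so the entry grade is on record, but 8.2.2 never refers to it.
- Where 8.2.2 wants an exception it writes one, for example for asymptomatic amylase or lipase elevation and for isolated thyroid or testosterone deficiency.

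**The case against.** The strongest answer is the hepatic algorithm in Appendix III, to which the liver table itself refers. It opens by telling the physician to rule out non-inflammatory causes and, where one is found, to treat it and carry on with immunotherapy. Gilbert disease is such a cause, and bilirubin already attributed to liver metastases probably is too. A sensible investigator would use this, and it suggests the sponsor does not want these patients held. It softens the problem in practice but does not settle it. Section 8.1 describes the algorithms as recommended guidance, whereas the sentence introducing the tables presents the tables as protocol-specific instructions. The two give different answers for the same patient.

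It is also fair to say that the conflict rests on cut-offs the protocol does not print, that baseline-relative grading would remove it, and that the text introducing the tables favours early withholding of drug. The first two points stand as conditions on the conclusion. The third supports caution when something has changed, which is not the case here.

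Two stronger readings are tempting and should not be drawn.

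- **A blocked first dose.** The calendar says "Labs completed prior to registration may be used for day 1 of cycle 1 tests if obtained" no more than 16 days before treatment. A reader might infer that one result can both qualify a patient and block the first dose, leaving the patient untreated, replaceable (12.3) and not evaluable (13.3). The tables do not support this. They govern continuing administration and the next dose, and the liver row speaks of restarting. The calendar note only avoids repeating tests.
- **The same defect for creatinine.** Entry on the clearance criterion can admit a creatinine above 1.5 x ULN. However, that table is titled "Creatinine increased, hematuria" under renal toxicity, and a stable pre-existing value is not plainly an increase. The argument also needs a further unprinted cut-off, and a patient whose clearance exceeds 45 mL/min despite the raised creatinine.

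**Conclusion.** The point holds for bilirubin, in patients already on initial or crossover treatment who were admitted above 1.5 and up to 3 x ULN because of Gilbert disease or liver metastases. Read as written, the liver table holds a stable patient and 8.2 then discontinues them. The conclusion depends on bilirubin being graded against ULN with a grade 1 ceiling below 3 x ULN. Under that assumption the required fall ranges from none to 50%, depending on ceiling and entry value.

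Severity is minor. The number of affected patients is not known and is probably small. A reader might infer a bias in the confirmed response rate or a loss of power, but the documents do not support that: a patient who has started treatment remains evaluable under 13.3, and there is no basis for estimating how many would be held. Nothing is claimed about ALT or AST, whose entry limit has no comparable allowance.

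**What to change.** Add one footnote to the liver table in 8.2.2, along these lines:

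*For patients registered or re-registered with bilirubin above 1.5 x ULN due to Gilbert disease or liver metastases, a bilirubin that has stayed at about the registration value, with no new ALT/AST elevation and no suspected immune-mediated hepatitis, does not by itself require a hold. After a hold, treatment may resume at grade 1 or less or on return to the registration value. Grade 3-4 removal is unchanged.*

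The conditions are deliberate. A value that fell on treatment and then climbed back may be a new event and should still prompt a hold, as should any suspicion of immune hepatitis. The sponsor should put a number on how close to the registration value counts as unchanged. It should also say whether a slight rise from an entry value near 3 x ULN counts as grade 3, since the footnote leaves removal at that grade in place. If baseline-relative handling is already intended, the footnote simply records it and brings the table into line with the hepatic algorithm.

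Cost: one footnote in an amendment and no new data, because registration and re-registration bilirubin are already required. The downside is slightly less conservative holding in a small subgroup, limited by the ALT/AST and suspected-hepatitis conditions.
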